8.3.3. Analysis of Heterologous Strains

HAI and Neut antibody responses against antigenically drifted variants of influenza A/H7 viruses (A/Shanghai/2/2013 and A/Guangdong/17SF003/2016) will be summarized for the Per Protocol population as described in Section 8 (Table 71 and Table 72; Figure 12, Figure 13, Figure 14, Figure 15, and Figure 16). A scatter plot of the correlation between response to the vaccine strain and each heterologous strain will be presented (Figure 17 and Figure 18). No formal hypothesis testing or modeling for the exploratory analysis of heterologous strains is planned.

8.3.4. NA Serum Antibody Responses

Descriptions of the NA assays and planned analyses will be described in an addendum to this SAP.

9. SAFETY EVALUATION

All summaries and analysis of safety data will be presented for the Safety Analysis Population. Safety summaries will be presented overall and grouped by treatment arm overall and by age stratum.

Continuous variables will be summarized using the following descriptive statistics: n (non-missing sample size), mean, standard deviation, median, maximum and minimum. All categorical measures will be summarized by the frequency and percentages of observed levels. The denominator for the percentages may be based on the number of non-missing observations for an assessment or based on the number of subjects in a population. This will be described for each table.

9.1. Demographic and Other Baseline Characteristics

Summaries of age, sex, ethnicity, race, BMI, and prior receipt of seasonal influenza vaccine will be presented by site (Table 21 and Table 22) and by treatment arm overall and by age stratum (Table 23, Table 24, Table 25, and Table 26). Age will be summarized as a continuous variable as well as by strata categories. Ethnicity is categorized as Hispanic or Latino, or not Hispanic and not Latino. In accordance with NIH reporting policy, subjects may self-designate as belonging to more than one race or may refuse to identify a race, the latter reflected in the electronic case report form (eCRF) as "No" to each racial option. BMI will be summarized as a continuous as well as categorical variable, categorized as (<30, ≥30). Self-reported history of prior receipt of seasonal influenza vaccine will be categorized as follows: neither 2016-2017 and 2017-2018, 2016-2017 only, 2017-2018 only, both 2016-2017 and 2017-2018, or unknown. Demographic information for individual subjects will be provided in Listing 6.

9.1.1. Prior and Concurrent Illnesses and Medical Conditions

All current illnesses and past or pre-existing medical conditions will be coded using Medical Dictionary for Regulatory Activities (MedDRA®) version 20.0 or higher.

Summaries of subjects' prior and concurrent medical conditions will be presented by treatment arm (Table 27 and Table 28).

Individual subject listings will be presented for all reported medical history including prior and concurrent medical conditions (Listing 7).

9.1.2. Prior and Concurrent Medications

Concomitant medications will be coded to the Anatomical Therapeutic Classification using the WHO Drug Dictionary. The use of concomitant medications during the study will be summarized by ATC1 and ATC2 code and treatment arm for the Safety population (Table 131 and Table 132). A listing of concomitant medications will be presented (Listing 16).

9.2. Measurements of Treatment Compliance

All subjects are to receive 2 study vaccinations administered in the clinic. The number of study vaccinations administered to subjects will be presented by treatment arm and by site,

overall and by age stratum in Table 19 and Table 20 and as part of the subject disposition tables (Table 17 and Table 18). Listing 1 presents subjects who received investigational product with randomized treatment arm and study product received for each vaccination.

9.3. Adverse Events

A summary of all adverse events is provided in Table 73. A summary of those events that occurred in \geq 5% of subjects in any treatment group is provided in Table 74.

9.3.1. Solicited Events and Symptoms

Systemic solicited adverse events were collected pre-vaccination, and systemic and local solicited adverse events were collected at-least 20 minutes post-vaccination and then daily for 7 days after each vaccination and graded on a scale of 0 (absent), 1 (mild), 2 (moderate) and 3 (severe). Systemic events include fever, feverishness, fatigue, malaise, myalgia, arthralgia, headache, and nausea. The grading scale for systemic events, including quantitative grading for fever, is included in Table 11. Local events include pruritus, ecchymosis, erythema, induration/swelling, pain, and tenderness. Ecchymosis, erythema, and induration are measured by both functional and measurement grading scales as defined in Table 10.

When calculating the incidence of solicited events, each subject will be counted once at the highest severity following the applicable vaccination, and any repetitions will be ignored. For summaries presented separately for each vaccination, the denominator for percentages will be the number of subjects who received the respective vaccination with non-missing data for the event summarized. For summaries over all vaccinations the denominator will be the number of subjects who received at least one vaccination with non-missing data for the event summarized.

The number and percentage of subjects reporting at least one solicited adverse event of any severity will be summarized for each solicited symptom, any systemic symptom, any local symptom, and any symptoms. For each event the denominator is the number of subjects who received the applicable vaccination with non-missing data for the specific event. The 95% CI calculated using Clopper-Pearson methodology from a binomial distribution (SAS Proc Freq with a binomial option) will be presented (Table 75, Table 76, Table 77, Table 78, Table 79, and Table 80). Logistic regression models will be fit to estimate the effect of treatment and age on the probability of reporting any local event or reporting any systemic event (Table 81 and Table 82). If statistically significant effects are observed in the model for local events or systemic events, then additional models will be fit for each individual event of that type.

$$logit[P(Event)] = \beta_0 + \beta_1 \times Treatment + \beta_2 (Age \ge 65) + \varepsilon,$$

For each systemic and local event, any systemic event, any local event, and any solicited event, the maximum severity over 7 days after each vaccination will be summarized for the Safety population. The number and percentage of subjects reporting each event will be summarized by the maximum severity and treatment group overall and by age stratum, separately for each vaccination and over all vaccinations. For each event the denominator is the number of subjects who received the applicable vaccination with non-missing data for the specific event. The 95% CI calculated using Clopper-Pearson methodology from a binomial

distribution (SAS Proc Freq with a binomial option) will be presented (Table 83, Table 84, Table 85, Table 86, Table 87, and Table 88).

The number of subjects reporting a solicited adverse event will be summarized for each day post vaccination for each vaccination and for all vaccinations combined both in a summary table (Table 89, Table 90, and Table 91) and graphically in a bar chart (Figure 19 and Figure 20). A comparison of the event rate for each treatment group between vaccination 1 and vaccination 2 will be presented, including p-values from McNemar's test performed within each age stratum and over all subject (Table 92 and Table 93).

Systemic and Local solicited events reported by subject will be presented in Listing 9 and Listing 10, sorted by subject ID, vaccination number, parameter, and study day.

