9.2.2 Reactogenicity

Reactogenicity events are AEs that are common and known to occur following administration of this type of study vaccine. The following Toxicity Grading Scales will be used to grade solicited local (injection site) and systemic (subjective and quantitative) reactions:

Injection Site Reactogenicity Grading

Injection Site Reaction	Mild (Grade 1)	Moderate (Grade 2)	Severe (Grade 3)
Pain – experienced without touching the injection site (spontaneous discomfort)	Subject is aware of pain, but it does not interfere with daily activity, and no pain medication is taken	Subject is aware of pain; there is interference with daily activity or it requires repeated use of a non-narcotic pain reliever for >24 hours	Subject is aware of pain, and it prevents daily activity or requires any use of a narcotic pain reliever

Injection Site Reaction	Mild (Grade 1)	Moderate (Grade 2)	Severe (Grade 3)
Tenderness – hurts only when injection site is touched or the arm is moved	The area immediately surrounding the injection site hurts only when touched or with arm motion, and it does not interfere with daily activity	The area immediately surrounding the injection site hurts when touched or with arm motion, and it interferes with daily activity	The area immediately surrounding the injection site hurts when touched or with arm motion, and it prevents daily activity
Pruritus (Itching)	Does not interfere with daily activity activity		Prevents daily activity
Ecchymosis (Bruising)* Does not interfere with daily activity		Interferes with daily activity	Prevents daily activity
Erythema (Redness)* Does not interfere with daily activity		Interferes with daily activity	Prevents daily activity
Induration Does not interfere with (Hardness)/Swelling* daily activity		Interferes with daily activity	Prevents daily activity

^{*} Will also be measured in mm but size will not be used as halting criteria.

Ecchymosis, erythema, and induration/swelling as analyzed by measurement will be graded as follows:

Local (Injection Site) Reactogenicity Measurements

Local (Injection Site) Reaction	Small	Medium	Large
Ecchymosis (Bruising)*	<20 mm	20 mm – 50 mm	>50 mm
Erythema (Redness)*	<20 mm	20 mm – 50 mm	>50 mm
Induration (Hardness)/Swelling*	<20 mm	20 mm – 50 mm	>50 mm

^{*} Will not be used as halting criteria.

Subjective Systemic Reactogenicity Grading

Systemic (Subjective)	Mild (Grade 1)	Moderate (Grade 2)	Severe (Grade 3)

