9.5 Halting Rules

Further enrollment and study vaccinations will be halted for DSMB review/recommendation if any of the following are reported:

- Any subject experiences ulceration, abscess, or necrosis at the injection site related to study product administration.
- Any 2 or more subjects experience laryngospasm, bronchospasm, or anaphylaxis within 1 day after administration of study product that is considered related to study product.
- Three or more subjects experience generalized urticaria (defined as occurring at more than two body parts) within 3 days after administration of study product that is considered related to study product.
- Any subject experiences a study vaccine-related SAE from the time of the first study vaccination through the subject's last study visit.
- Any subject experiences acute weakness of limbs and/or cranial nerve innervated muscles (description of potential signal of GBS) after administration of study product.
- Any subject develops a PIMMC after administration of study product.

This trial will also be halted for DSMB review/recommendation if, within 7 days after administration of either study vaccination, any of the following occurs within the AS03-adjuvanted treatment arms or within the two unadjuvanted treatment arms.

• 7% or more of subjects (with a minimum of 3 subjects) who received at least one dose of study vaccine to date, cumulative to both vaccine administration, across all groups, experience the same severe (Grade 3) study vaccine-related injection site reaction.

Ecchymosis, erythema, and induration/swelling will also be measured in mm but size will not be used as halting criteria.

- 7% or more of subjects (with a minimum of 3 subjects) who received at least one dose of study vaccine to date, cumulative to both vaccine administration, across all groups, experience the same severe (Grade 3) study vaccine-related subjective systemic reaction, for which the severity (grade) is corroborated by study personnel.
- 7% or more of subjects (with a minimum of 3 subjects) who received at least one dose of study vaccine to date, cumulative to both vaccine administration, across all groups, experience the same severe (Grade 3) study vaccine-related quantitative systemic reaction.

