12. SUMMARY OF CHANGES IN THE CONDUCT OF THE STUDY OR PLANNED ANALYSES

This SAP does not include any changes from the analyses described in the protocol.

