Symptom	Severity	n	%	95% CI	n	%	95% CI	n	%	95% CI	n	%	95% CI	n	%	95% CI
Erythema	None	х	XX	xx-xx	X	XX	xx-xx	X	XX	xx-xx	х	XX	xx-xx	X	XX	xx-xx
	Mild	х	xx	xx-xx	Х	XX	xx-xx	Х	XX	xx-xx	х	xx	xx-xx	Х	XX	xx-xx
	Moderate	х	xx	xx-xx	X	xx	xx-xx	X	XX	xx-xx	х	xx	xx-xx	X	XX	xx-xx
	Severe	х	XX	xx-xx	X	XX	xx-xx	X	XX	xx-xx	х	XX	xx-xx	X	XX	xx-xx
Erythema (measurement)	None	х	XX	xx-xx	X	xx	xx-xx	х	XX	xx-xx	Х	XX	XX-XX	Х	XX	XX-XX
	Mild	х	XX	xx-xx	X	XX	xx-xx	X	XX	xx-xx	х	XX	xx-xx	X	XX	xx-xx
	Moderate	х	XX	xx-xx	X	XX	xx-xx	X	XX	xx-xx	х	XX	xx-xx	X	XX	xx-xx
	Severe	х	XX	xx-xx	X	XX	xx-xx	X	XX	xx-xx	х	XX	xx-xx	X	XX	xx-xx
Induration/Swelling	None	х	XX	xx-xx	X	XX	xx-xx	X	XX	xx-xx	х	XX	xx-xx	X	XX	xx-xx
	Mild	х	XX	xx-xx	X	XX	xx-xx	X	XX	xx-xx	х	XX	xx-xx	X	XX	xx-xx
	Moderate	Х	xx	xx-xx	X	XX	xx-xx	х	XX	xx-xx	х	XX	xx-xx	х	XX	xx-xx
	Severe	X	XX	xx-xx	X	XX	xx-xx	X	XX	xx-xx	х	XX	xx-xx	X	XX	xx-xx
Induration/Swelling (measurement)	None	Х	XX	XX-XX	X	XX	xx-xx	X	XX	xx-xx	Х	XX	xx-xx	X	XX	xx-xx
	Mild	х	xx	xx-xx	X	XX	xx-xx	X	xx	xx-xx	х	XX	xx-xx	X	XX	xx-xx
	Moderate	х	xx	xx-xx	X	XX	xx-xx	X	xx	xx-xx	х	XX	xx-xx	X	XX	xx-xx
	Severe	Х	xx	xx-xx	X	XX	xx-xx	х	xx	xx-xx	х	XX	xx-xx	х	XX	xx-xx

N = Number of subjects in the Safety Population who received any study vaccination.

Severity is the maximum severity reported over all solicited symptoms post dosing for each subject.

^{95%} CI estimated using Clopper-Pearson exact method

Table 84: Number and Percentage of Subjects Experiencing Solicited Events by Symptom, Maximum Severity and Treatment Arm Post Study Vaccination 1 – Safety Population *

[Footnote Update] N = Number of subjects in the Safety Analysis Population who received the first study vaccination.

Table 85: Number and Percentage of Subjects Experiencing Solicited Events by Symptom, Maximum Severity and Treatment Arm Post Study Vaccination 2 – Safety Population *

[Footnote Update] N = Number of subjects in the Safety Analysis Population who received the second study vaccination.

Table 86: Number and Percentage of Subjects Experiencing Solicited Events by Symptom, Maximum Severity, Treatment Arm and Age Stratum Post Any Study Vaccination – Safety Population *

		3.75	Group 5 mcg A/2 + AS03 (N=X)	H7N9 3	7.5	Group 2 mcg A/H + AS03 (N=X)		15	Group 3 mcg A/H + AS03 (N=X)		15	Group 4 mcg A/H' (N=X)		45	Group 5 mcg A/H (N=X)	; 7N9
Symptom	Severity	n	%	95% CI	n	%	95% CI	n	%	95% CI	n	%	95% CI	n	%	95% CI
							Age 19	-64								•
Any Symptom	None	X	XX	xx-xx	X	XX	xx-xx	X	xx	xx-xx	X	XX	xx-xx	X	XX	xx-xx

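### The SAP relabels the millimetre size of local reactions as severity Grades 1–3, so a large reaction that the protocol grades Mild is tabulated as Severe

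*SAP*

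**What the plan says.** **Protocol.** Section 9.2.2 has two tables for these three reactions. The grading table has columns Mild (Grade 1), Moderate (Grade 2) and Severe (Grade 3), defined by whether the reaction does not interfere with, interferes with, or prevents daily activity. The Mild entry for redness, for example, is "Erythema (Redness)* Does not interfere with daily activity". A note to that table says of size: "Will also be measured in mm but size will not be used as halting criteria". The second table is introduced by "Ecchymosis, erythema, and induration/swelling as analyzed by measurement will be graded as follows" and has columns Small (<20 mm), Medium (20–50 mm) and Large (>50 mm), with no grade number and no severity word. Section 9.5 repeats the halting exclusion: "Ecchymosis, erythema, and induration/swelling will also be measured in mm but size will not be used as halting criteria".

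**SAP.** Section 9.3.1 says "Ecchymosis, erythema, and induration are measured by both functional and measurement grading scales as defined in Table 10". Table 10 keeps the protocol's cut-offs but heads the size columns Small (Grade 1), Medium (Grade 2) and Large (Grade 3). The same section fixes what the grade numbers mean (solicited events are "graded on a scale of 0 (absent), 1 (mild), 2 (moderate) and 3 (severe"). The Table 83, 86 and 89 shells list ecchymosis, erythema and induration/swelling twice, once by function and once marked as measurement. Both versions take the levels None, Mild, Moderate and Severe. Tables 84, 85, 87, 88, 90 and 91 follow the same formats. The footnote to Tables 83 and 86 reads "Severity is the maximum severity reported over all solicited symptoms post dosing for each subject". SAP 12 states: "This SAP does not include any changes from the analyses described in the protocol".

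**The concern.** The protocol nowhere equates a Large reaction with a Severe one. That equation first appears in SAP Table 10 and is carried into the shells, while SAP 12 says the analyses are unchanged. One reaction can therefore hold two different severities in the same table, and the line that combines symptoms may take the higher one.

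Solicited reactogenicity is a primary safety outcome. Protocol 9.1 assesses safety by severity as well as frequency, and protocol 11.6.2 plans summaries by daily and maximum severity. A reader of Tables 83–88 would take a Severe count as reactions that prevented daily activity, when some could be reactions that were only large. Protocol 2.3.1 reports that redness and swelling were more frequent and more severe with GSK's AS03-adjuvanted vaccines, so any shift would be expected to fall more on the adjuvanted arms. The documents do not say by how much.

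**Working it through.** There is no planned figure to reproduce, because neither document gives a rate of severe or of large local reactions. The check has two parts.

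**1. Apply both sets of rules to test cases.** Inputs: the functional scale and size classes in protocol 9.2.2, the size grades in SAP Table 10, and the maximum rule in the Table 83/86 footnote, which excludes no row. The last column is the larger of the two grades.

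| Effect on daily activity | Size | Protocol severity grade | SAP measurement grade | SAP Any Local Symptom, literal footnote |
|---|---|---|---|---|
| does not interfere | 10 mm | 1 | 1 | 1 |
| does not interfere | 35 mm | 1 | 2 | 2 |
| does not interfere | 60 mm | 1 | 3 | 3 |
| interferes | 60 mm | 2 | 3 | 3 |
| prevents | 10 mm | 3 | 1 | 3 |

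The second, third and fourth cases receive a higher severity under the SAP. The raised grade in the measurement row comes directly from Table 10 and the shells. The raised grade in the composite depends on the footnote.

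**2. Bound the effect on the composite Severe line.** Let f be the proportion with a severe local reaction by function and s the proportion with any measured reaction over 50 mm. The composite proportion is f + s minus the proportion with both, so:

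- lower bound (full overlap): max(f, s)
- upper bound (no overlap): f + s
- if independent: 1 − (1 − f)(1 − s)

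Inflation over f therefore runs from max(0, s − f) to s. The rates below are assumptions chosen only to show the range.

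| f | s | Full overlap | Independent | No overlap | Inflation (points) |
|---|---|---|---|---|---|
| 1% | 2% | 2.0% | 1 − 0.99×0.98 = 3.0% | 3.0% | 1.0 to 2.0 |
| 2% | 5% | 5.0% | 1 − 0.98×0.95 = 6.9% | 7.0% | 3.0 to 5.0 |
| 3% | 2% | 3.0% | 1 − 0.97×0.98 = 4.9% | 5.0% | 0 to 2.0 |
| 3% | 8% | 8.0% | 1 − 0.97×0.92 = 10.8% | 11.0% | 5.0 to 8.0 |

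In an adjuvanted arm of 160 (protocol 11.4.3), the second row moves from about 3 subjects (160 × 0.02 = 3.2) to between 8 (160 × 0.05) and about 11 (160 × 0.07 = 11.2). The third row shows that there may be no inflation at all.

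**What does not move.** A reaction with a measurable size already meets at least the Mild functional definition, provided both scales are recorded consistently. Any-versus-none classification then stays the same. The incidence tables (75–80), the Table 81 logistic model for any local event, and the McNemar comparisons in Tables 92 and 93 (no symptoms versus mild or greater) should be essentially unaffected.

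**The case against.** The best defence has four parts.

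- **No sentence puts the measurement rows into the composite.** SAP 9.3.1 lists six local events, and measurement is a second scale for three of them, not an additional symptom. This stands in part: inclusion in Any Local Symptom follows from a literal footnote and the absence of any exclusion, not from an express rule. But the shells list the measurement rows in the symptom column, so a programmer could fairly include them. The measurement rows print Severe either way.
- **The protocol itself says that size is graded.** It does, in "Ecchymosis, erythema, and induration/swelling as analyzed by measurement will be graded as follows", but the classes that follow are Small, Medium and Large. Excluding size from halting does not turn it into a severity grade elsewhere.
- **Nothing is lost.** The functional rows are kept beside the measurement rows, and Listing 10 gives subject-level severity. This is correct for single symptoms. The composite line, however, cannot be rebuilt from the separate rows without subject-level data.
- **The primary result is untouched.** The primary endpoint is occurrence, and protocol 11.6.2 analyses it as none versus any severity. This stands.

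A reader might also infer that the tables would conflict with the halting rule. That inference is weak. Protocol 9.5 counts the same Grade 3 vaccine-related reaction, symptom by symptom, so a composite over symptoms would not match that count on either scale. The functional rows that do correspond are still tabulated.

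**Conclusion.** The discrepancy is real and undeclared. Under the SAP, a reaction over 50 mm that does not interfere with activity is tabulated as Severe in its measurement row, although the protocol grades it 1. On the literal footnote, the same label passes to Any Local Symptom and Any Symptom. The effect is confined to the severity distributions in Tables 83–91 and Figure 20.

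Its size is unknown. The composite Severe line rises by between nothing (full overlap with s no larger than f) and s. Three stronger readings might be drawn, and the documents do not support them:

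- that the primary endpoint changes, which it should not, because it is occurrence;
- that the leading safety result is distorted, when the safety table marked topline (Table 73) reports solicited local events with no split by severity;
- that the severe rate is inflated by a particular multiple, which would need rates and an overlap that the documents do not give.

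The conclusion for the composite line rests on the literal reading of the footnote. The conclusion for the measurement rows needs no such reading.

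**What to change.** 1. In SAP Table 10, remove Grade 1/2/3 from the headings of the measurement scale and leave Small, Medium and Large.
2. In Tables 83–91, label the measurement rows None/Small/Medium/Large.
3. In the footnotes to those tables, and in the note for Figure 20, state that severity for Any Local Symptom and Any Symptom is the maximum over the functional local grades and the systemic grades only.
4. Keep the size distribution as separate descriptive rows.

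With these edits the SAP 12 statement becomes accurate on this point. The cost is SAP wording and shell changes; no new data, visit or procedure is needed. The one downside is that size no longer feeds the composite severity line, so a large reaction that does not interfere with activity will show its size only in the measurement rows.
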